9.5.3.2. Part C

In Part C, the immunogenicity analysis of BD vaccine response will be performed using the noninferiority tests of the 2 null hypotheses based on the 2 key secondary endpoints, respectively. Further considerations for immunogenicity analyses are provided in the SAP.

Part C Key Secondary Endpoint 1: Ab GMT at BD-Day 29

Hypothesis: immunogenicity response to mRNA-1273 BD as measured by Ab GMT at BD-Day 29 in Part C is noninferior compared with Ab GMT at Day 57 (28 days after second dose) in the primary series of mRNA-1273.

The noninferiority of post-booster GMT at BD-Day 29 in Part C as compared to the primary series at Day 57 is considered to be demonstrated if the lower bound of the 95% CI of the GMR (ratio of GMT at BD-Day 29 vs. GMT at Day 57 [28 days after Dose 2 of the primary series]) is ≥ 0.67 using a noninferiority margin of 1.5 (1.5-fold immuno-bridging margin for the lower bound of the 95% CI for GMT ratio/GMR).

The GMT with 95% CI will be summarized using t-distribution of the log transferred values and then back transformed to the original scale. The GMR with 95% CI to compare post-booster GMT at BD-Day 29 in Part C with the primary series GMT at Day 57 (28 days after the second dose) will be computed based on the t-distribution of mean difference in the log transferred values and then back transformed to the original scale.

Part C Key Secondary Endpoint 2: Ab Seroresponse Rate at BD-Day 29

Hypothesis: immunogenicity response to mRNA-1273 BD as measured by seroresponse rate (SRR) at BD-Day 29 in Part C is noninferior compared with SRR of the primary series at Day 57 (28 days after second dose of the primary series of mRNA-1273).

The noninferiority in SRR post-booster at BD-Day 29 in Part C compared with SRR of the primary series at Day 57 (28 days after the second dose of the primary series of mRNA-1273) is considered to be demonstrated if the lower bound of the 95% CI of the SRR difference (SRR of the booster at BD-Day 29 – SRR of the primary series at Day 57) is $> -10\%$ (using the noninferiority margin of 10%). The SRR difference is defined as the seroresponse rate at BD-Day 29 in Part C minus the seroresponse rate at Day 57 (28 days after the second dose) following the primary series of mRNA-1273. The seroresponse of a booster or the primary series is defined as a titer change from baseline (pre-Dose 1 in primary series) below the LLOQ to $\geq 4 \times$ LLOQ, or at least a 4-fold rise if baseline is \geq LLOQ.

The SRR with 95% CI (using Clopper-Pearson method) will be provided. The SRR difference with 95% CI to compare post-booster SRR at BD-Day 29 in Part C with the primary series SRR at

Day 57 (28 days after the second dose) will be computed. The method for computing 95% CI of seroresponse rate difference will be provided in the SAP.

The primary immunogenicity objective in Part C is met if noninferiority is demonstrated based on both key secondary endpoints (both GMT and SRR) .

9.5.4. Exploratory Analyses in Part A

The endpoint of viral infection kinetics will be assessed by determining the number of days until testing of saliva samples becomes negative after COVID-19 is established.

The endpoint of duration of symptoms will be assessed by determining the total number of days that a study participant with COVID-19 remains symptomatic through daily assessments after diagnosis.

Vaccine efficacy to prevent all-cause mortality will be assessed by similar analysis methods as used for the primary endpoint analysis, using PP Set, mITT Set, and FAS. All deaths, regardless of cause from the time of randomization, will be included. If the number of deaths becomes large enough to warrant analysis, the same Cox proportional hazard model described above for the primary objective will be applied using the PP Set, the mITT Set, and the FAS. Death, regardless of cause, from randomization will be included.

This endpoint of burden of disease (BOD) is defined based on the post SARS-CoV-2 infection follow-up. A BOD score will be used to reflect the severity of symptoms with maximum score at COVID-19 death ([Table 14](#)).

Table 14: Burden of Disease Score

Patient State	BOD Score
Uninfected/Asymptomatic infection	0
Symptomatic without hospitalization	1
Hospitalization	2
Death	3

Abbreviation: BOD = burden of disease.

9.5.5. Subgroup Analyses

To determine whether the VE is consistent across various subgroups, the VE and its 95% CI may be estimated using the similar model within each category of the following classification variables.

- Age groups: ≥ 18 , < 65 , and ≥ 65
- Age and health risk for severe disease: ≥ 18 and < 65 and not at risk; ≥ 18 and < 65 and at risk, and ≥ 65

- Sex (female, male)
- Race
- At risk for severe COVID-19 illness ([Section 6.2.1.1](#))

Subgroup analysis for the long-term efficacy may be performed descriptively by treatment cohort within above categories.

9.6. Interim Analyses

In Part A, there are 2 planned IAs at 35% and 70% of total target cases across the 2 treatment groups. The primary objective of the IAs is for early detection of reliable evidence that VE is above 30%. The Lan-DeMets O'Brien-Fleming approximation spending function is used for calculating efficacy bounds and to preserve the (1-sided) 0.025 false positive error rate over the IAs and the primary analysis (when the target number of cases have been observed), relative to the hypothesis: $H_0^{\text{efficacy}}: HR \geq 0.7$ (equivalently, proportional hazards $VE \leq 0.3$).

There is no intention to stop the study early if the efficacy has been demonstrated at any of the IAs. If efficacy is demonstrated at an IA, the subsequent IA or primary analysis will be considered supportive in nature. The DSMB will review the IA results and make recommendations to the Sponsor in terms of study results reporting and unblinding based on the boundaries of early efficacy as described in this section, safety data, and data external to this study. In addition to possible early efficacy at IAs, the DSMB will monitor for non-efficacy and vaccine harm; the guiding principles (non-binding) is provided in [Section 8.4.2](#), and the details will be provided in the SAP.

[Table 15](#) summarizes the timing, number of cases and decision guidance at each IA and primary analysis.

The first IA will occur when approximately 35% of the total cases have been observed (across both treatment groups). The study will be considered positive at the first IA if the p-value for rejecting $HR \geq 0.7$ is less than 0.0002 based on the Lan-DeMets O'Brien-Fleming approximation spending function. This corresponds to an observed HR of approximately 0.259, or an observed VE approximately 0.741.

The second IA will occur when approximately 70% of the total cases have been observed. The study will be considered positive (VE has been demonstrate) if the p-value for rejecting $HR \geq 0.7$ is less than 0.0073 based on the Lan-DeMets O'Brien-Fleming approximation spending function. This corresponds to an observed HR of approximately 0.435, or an observed VE of approximately 0.565.

The primary analysis will be performed when approximately 151 cases have been observed in the study. The study will be considered positive at the primary analysis if the 1-sided p-value for rejecting $HR \geq 0.7$ is less than 0.0227. This corresponds to an observed HR of approximately 0.505 or observed VE of approximately 0.495.

Table 15: Interim Boundaries Using O’Brien-Fleming Spending Function, Calculation Based on the PP Set for the Primary Efficacy Endpoint

Information Fraction (% of total #cases)	Number of Cases	Nominal Alpha	Efficacy Boundary Rejecting H0: VE \leq 30%	Cum Prob (crossing efficacy boundary if the true VE = 60%)
IA1 35%	53	0.0002	VE \geq 0.741 (HR \leq 0.259)	4.6%
IA2 70%	106	0.0073	VE \geq 0.565 (HR \leq 0.435)	61.5%
Primary analysis 100%	151	0.0227	VE \geq 0.495 (HR \leq 0.505)	90.0%

Abbreviations: HR = hazard ratio; IA: = interim analysis; PP = per-protocol; VE = vaccine efficacy.

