9.3. Sample Size Determination

The sample size is driven by the total number of cases to demonstrate VE (mRNA-1273 vs. placebo) to prevent COVID-19 in Part A. Under the assumption of proportional hazards over time and with 1:1 randomization of mRNA-1273 and placebo, a total of 151 COVID-19 cases will provide 90% power to detect a 60% reduction in hazard rate (60% VE), rejecting the null hypothesis H_0 : VE $\leq 30\%$, with 2 IAs at 35% and 70% of the target total number of cases using a 1-sided O'Brien-Fleming boundary for efficacy and a log-rank test statistic with a 1-sided false positive error rate of 0.025. The total number of cases pertains to the PP Set accruing at least 14 days after the second dose. There are 2 planned IAs in this study, which will be performed when approximately 35% and 70% of the target total number of cases have been observed. Approximately 30,000 participants will be randomized with the following assumptions:

- The target VE against COVID-19 is 60% (with 95% CI lower bound ruling out 30%, rejecting the null hypothesis H_0 : VE $\leq 30\%$)
- A 6-month COVID-19 incidence rate of 0.75% in the placebo arm
- An annual dropout rate of 2% (loss of evaluable participants)
- Two IAs at 35% and 70% of total target cases across the 2 treatment groups with O'Brien-Fleming boundaries for efficacy monitoring
- 3-month uniform accrual
- Approximately 15% of participants will be excluded from the PP population, and participants are at risk for COVID-19 starting 14 days after the second dose

[Table 6](#) provides sample size with 90% power to demonstrate VE on COVID-19.

Table 6: Conditions and Sample Size to Demonstrate Vaccine Efficacy

Target VE	Lower Bound	Randomization Ratio	Total # of Cases	6-Month Incidence Rate		Total Sample Size ^a
				Placebo	mRNA-1273	
--	--	--	--			--
60%	30%	1:1	151	0.75%	0.30%	30,000

Abbreviations: IP = investigational product; PP = Per Protocol; VE = vaccine efficacy.

[figure not shown]
^a Sample size to account for 15% participants to be excluded from the PP Set (eg, seropositive at baseline, have not received planned IP).

The sample size is calculated using R package gsDesign ([Anderson 2020](#)).

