6.3.1.2. Primary Analysis Approach

The number and percentage of subjects who had an event (i.e. the first occurrence of COVID-19 starting 14 days after the second injection, date of documented COVID-19 – date of the second injection ≥ 14) and subjects who were censored will be summarized.

The non-parametric Kaplan-Meier method will be used to estimate the time to first occurrence of COVID-19 curve in each treatment group.

Vaccine efficacy (VE) is defined as the percent reduction in the hazard of the primary endpoint (mRNA-1273 vs. placebo), i.e. one minus the hazard ratio (HR). The null hypothesis is:

$$H_0^{\text{efficacy}}: \text{vaccine efficacy} \leq 0.3$$

Equivalently, the null hypothesis is:

$$H_0^{\text{efficacy}}: \text{hazard ratio (HR)} \geq 0.7$$

A stratified Cox proportional hazard (PH) model with Efron's method of tie handling and with treatment group as covariate will be used to assess the magnitude of the treatment group difference (i.e. HR) between mRNA-1273 vs. placebo. The same stratification

factors used for randomization ([Section 4.4](#)) will be applied to the stratified Cox model. VE with corresponding alpha-adjusted confidence interval (CI), 95% CI, and one-sided p -value for testing the null hypothesis from the stratified Cox model would be reported at a planned interim analysis up to the analysis at which vaccine efficacy is demonstrated. After vaccine efficacy was demonstrated, VE and 95% CI would be provided for subsequent analysis/updates of efficacy.

In this study, vaccine efficacy was demonstrated based on pre-specified statistical criterion (Section 6.4) at the first interim analysis, at which, one-sided p -value for testing the null hypothesis of $VE \leq 0.3$, 95% CI and alpha-adjusted CI were provided from the stratified Cox model. At the primary analysis where the total number of COVID-19 cases > 151 , total target number of cases, VE, one-sided p -value for testing the null hypothesis of $VE \leq 0.3$ and 95% CI were provided. In subsequent analysis/updates of efficacy, VE and 95% CI will be provided.

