6.4. Planned Analyses and Analyses of Efficacy Analyses that Have Been Conducted

6.4.1. Planned Interim Analyses and Primary Analysis

There were two planned interim analyses in this study, which would be performed when approximately 35% and 70% of the target total number of COVID-19 cases across the two vaccine groups had been observed respectively. The primary objective of the IAs was for early detection of reliable evidence that VE is above 30%. The Lan-DeMets O'Brien-Fleming approximation spending function was used for calculating efficacy bounds and to preserve the (1-sided) 0.025 false positive error rate over the two IAs and the primary analysis (when the target number of cases have been observed), relative to the null hypothesis (H_0^{efficacy} : $VE \leq 30\%$). There is no intention to stop the study early if the efficacy had been demonstrated at any of the IAs. If efficacy was demonstrated at an IA, the subsequent IA or primary analyses would be considered supportive in nature. The IA results would be reviewed by the DSMB.

The first IA would occur when 35% of the total cases in the PP set had been observed. The study would be considered positive at this IA if the one-sided p -value for rejecting $VE \leq$

30% ($HR \geq 0.7$) was less than 0.0002 based on the Lan-DeMets O'Brien-Fleming approximation spending function. This corresponds to an observed HR of approximately 0.259, or an observed VE approximately 0.741.

The second IA would occur when 70% of the total cases have been observed in the PP set. The study will be considered positive at this IA if the p -value for rejecting $VE \leq 30\%$ ($HR \geq 0.7$) was less than 0.0073 based on the Lan-DeMets O'Brien-Fleming approximation spending function. This corresponds to an observed HR of approximately 0.435, or an observed VE of approximately 0.565.

The primary analysis would be performed when approximately 151 cases have been observed in the PP Set. The study would be considered positive at the primary analysis when a total of 151 cases had been observed and if the one-sided p -value for rejecting $HR \geq 0.7$ was less than 0.0227. This corresponds to an observed hazard ratio of approximately 0.505 or observed VE of approximately 0.495.

An independent, unblinded statistics team would carry out the IAs. The unblinded statistics team would not be involved in either study design or the regular study conduct. The subjects and study sites will remain blinded throughout the study.

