The final analysis would be performed after all subjects have completed the study and after the database is cleaned and locked. Results of this analysis would be presented in a CSR.

The timing, number of cases and decision guidance at each IA and primary analysis is summarized in the table below (Table 13 of the protocol).

Table 4: Interim Boundaries Using O’Brien-Fleming Spending function, Calculation Based on the PP Set for the Primary Efficacy Endpoint

Information fraction (% of total #cases)	Number of cases	Nominal Alpha	Efficacy Boundary Rejecting H ₀ : VE ≤ 30% (HR ≥ 0.7)	Cum Prob (crossing efficacy boundary if the true VE = 60%)
IA1 35%	53	0.0002	VE ≥ 0.741 (HR ≤ 0.259)	4.6%
IA2 70%	106	0.0073	VE ≥ 0.565 (HR ≤ 0.435)	61.5%
Primary analysis 100%	151	0.0227	VE ≥ 0.495 (HR ≤ 0.505)	90.0%

Abbreviations: HR = hazard ratio; IA: interim analysis; PP = per-protocol; VE = vaccine efficacy.

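### The HR/VE boundary column and the Table 7 powers use Var(log HR) = 4/d, which is not the basis of the 151 cases: Table 7 overstates power for severe COVID-19, and the printed HR limits are too lenient at both interim analyses.

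*Protocol*

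**What the plan says.** Protocol 9.6 defines success at each look by a one-sided p-value for HR ≥ 0.7 and translates it into an observed effect. At IA1 (53 cases, p below 0.0002): "This corresponds to an observed HR of approximately 0.259, or an observed VE approximately 0.741". At IA2 (106 cases, p below 0.0073) the values are HR 0.435 and VE 0.565. At the primary analysis (151 cases, p below 0.0227): "This corresponds to an observed HR of approximately 0.505 or observed VE of approximately 0.495". The protocol says that Table 15 "summarizes the timing, number of cases and decision guidance at each IA and primary analysis"; it prints nominal alpha and VE/HR boundary in adjacent columns, with cumulative crossing probabilities of 4.6%, 61.5% and 90.0% at a true VE of 60%. SAP (Part A) 6.4.1 and its Table 4 repeat all of this ("This corresponds to an observed hazard ratio of approximately 0.505 or observed VE of approximately 0.495").

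Protocol 9.3 derives 151 cases for 90% power from "a log-rank test statistic with a 1-sided false positive error rate of 0.025" and adds: "The sample size is calculated using R package gsDesign". No variance formula is given. Protocol 9.3.1, Table 7, gives power for severe COVID-19 at 30 and 60 cases; SAP 4.3 sends the reader there.

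The p-value that decides is a Cox p-value. SAP 6.3.1.2 refers to a one-sided p-value "for testing the null hypothesis from the stratified Cox model would be reported at a planned interim analysis". Protocol 9.5.1.1 describes a score-based interval for that model, whereas Table 26 (11.4.2) specifies a Wald test.

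**The concern.** The figures in one design should rest on one variance, or say where they do not. If the HR/VE column is on a different footing from the test that yields the p-value, two adjacent columns of a table offered as decision guidance can give opposite answers for the same data. If Table 7 is on a different footing from the 151 cases, the documents' only statement of power for severe COVID-19 is not comparable with the primary power statement. What is at stake is the accuracy of stated thresholds and powers.

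**Working it through.** **Inputs.** HR 0.7 under the null, 0.4 under the alternative; 1:1 allocation; one-sided 0.025; looks at 35%, 70% and 100% of 151 (52.85, 105.7 and 151 cases); Lan-DeMets O'Brien-Fleming spending (Protocol 9.3 and 9.6). Table 7 scenarios from Protocol 9.3.1.

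**1. Nominal alphas.** The bounds are z = 3.613, 2.441 and 2.000, i.e. p = 0.00015, 0.0073 and 0.0227. These match Table 15.

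**2. HR column.** With Var(log HR) = 4/d the limit is 0.7 × exp(−2z/√d), which gives 0.2591, 0.4354 and 0.5055. This is the printed 0.259/0.435/0.505.

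**3. The 151 cases and the crossing probabilities.** Drift 3.264 at full information gives 4.6/61.5/90.0%, as printed. ln(0.7/0.4) = ln 1.75 = 0.5596.
- Under 4/d, the cases needed are 4 × 3.264² / 0.5596² ≈ 136. With 151 cases the drift is 0.5596 × √151 / 2 = 3.438, which gives 5.7/66.9/92.7%.
- With event-split variances V = (1 + HR)²/HR: V0 = 1.7²/0.7 = 4.129 and V1 = 1.4²/0.4 = 4.900. Then (1.960√V0 + 1.282√V1)² / 0.5596² = 148.5. Multiplying by the group-sequential inflation 3.264²/(1.960 + 1.282)² = 1.014 gives 150.6.

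So the event-split variance reproduces 151, and 4/d does not.

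**4. Table 7.** Under 4/d, power = Φ(ln(HR0/HR1)√d/2 − 1.960). Example, 30 cases, VE 60% against ≤ 0%: 0.9163 × √30 / 2 − 1.960 = 0.549, power 70.9%, as printed. On the event-split basis, power = Φ((ln(HR0/HR1)√d − 1.960√V0)/√V1). Same cell: (5.019 − 3.920)/2.214 = 0.496, power 69.0%.

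| Cases | True VE | Null VE ≤ | Printed (4/d) | Event-split | Binomial score |
|---|---|---|---|---|---|
| 30 | 60% | 0% | 70.9 | 69.0 | 66.6 |
| 30 | 60% | 10% | 60.3 | 59.2 | 54.5 |
| 30 | 60% | 20% | 47.5 | 47.3 | 40.9 |
| 30 | 70% | 0% | > 90 (90.9) | 87.0 | 88.0 |
| 30 | 70% | 10% | 85.3 | 81.1 | 79.8 |
| 30 | 70% | 20% | 76.6 | 72.6 | 67.9 |
| 60 | 60% | 10% | 88.1 | 85.6 | 85.5 |
| 60 | 60% | 20% | 76.6 | 74.0 | 71.4 |

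The other cells printed as above 90% stay at or above 91.3% on the event-split basis.

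**5. The printed HR against the Cox p-value.** With rare events, equal person-time and no stratification, a vaccine and b placebo cases give HR = a/b. Let p0 = 0.7/1.7 and q0 = 1 − p0.
- Wald: z = ln(0.7/HR)/√(1/a + 1/b).
- Score: z = (d·p0 − a)/√(d·p0·q0).

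At HR 0.259 the 53 cases split about 10.9:42.1. The Wald variance is 1/10.9 + 1/42.1 = 0.115, against 4/53 = 0.075. Hence Wald z = 0.994/0.340 = 2.93 (p = 0.0017) and score z = (21.82 − 10.90)/3.583 = 3.05 (p = 0.0012), against 0.0002. At the printed HRs for IA2 and the primary analysis, p (score/Wald) is 0.0115/0.0122 against 0.0073 and 0.0285/0.0291 against 0.0227.

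Attainable splits:

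| Look | Split | VE | Meets VE column | p score | p Wald | Nominal alpha |
|---|---|---|---|---|---|---|
| IA1 | 10:43 | 0.767 | yes | 0.00048 | 0.00085 | 0.0002 |
| IA1 | 9:44 | 0.795 | yes | 0.00017 | 0.00039 | 0.0002 |
| IA2 | 32:74 | 0.568 | yes | 0.0108 | 0.0114 | 0.0073 |
| IA2 | 31:75 | 0.587 | yes | 0.0063 | 0.0068 | 0.0073 |
| Primary | 50:101 | 0.505 | yes | 0.0220 | 0.0226 | 0.0227 |
| Primary | 51:100 | 0.490 | no | 0.0323 | 0.0329 | 0.0227 |

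**6. Cause of the leniency.** Putting the boundary column on the design's own null variance, 0.7 × exp(−z√(4.129/d)), gives only 0.255/0.432/0.503. No attainable IA1 split changes; at IA2 the 32:74 split (HR 0.432) sits on the limit.

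**The case against.** The documents say approximately each time, make the p-value the success criterion, and treat the boundaries as guidelines (Protocol 8.4.2). The 53-case look never took place: IA1 had 95 cases, and p < 0.0001 was compared with a recomputed alpha of 0.0047 (SAP 6.4.2.1). The Part B and Part C SAP, section 1, records the Part A analyses as complete. No document says that Table 7 shares a formula with Table 6, and three of its seven numeric cells move by less than 2 points. Log-rank and Cox score tests belong to one family, so only the Wald wording in Table 26 stands apart. Corrected boundaries are not determinate either: 9:44 at IA1 passes by score and fails by Wald, and against the unrounded alpha of 0.00015 it fails by score as well.

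Most of this stands. It rules out any effect on conduct or conclusions, and it is a good reason to annotate the boundary column and not replace it. It does not remove the discrepancy. A p-value of 0.0012 to 0.0017 where 0.0002 is stated is 6 to 8.5 times too large, which three-decimal HRs marked approximate do not convey, and Table 7 carries no such caveat.

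A reader might infer that the mixing of bases makes the HR limits lenient. Step 6 shows that it does not, as such: the leniency comes from a normal approximation used away from a 50:50 split. A reader might also infer that only IA1 is affected. The 32:74 split at IA2 shows otherwise.

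**Conclusion.** The point holds as a minor correction of stated figures. The 4/d attribution is inferred by re-derivation, since neither document states a formula, but it reproduces all three HR limits and all seven numeric Table 7 powers.

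- Table 7 overstates power by 0.2 to 4.2 points on the basis that reproduces the 151 cases, and the cell for VE 70% against ≤ 0% at 30 cases belongs below 90% (87.0%; 88.0% by score).
- The HR/VE column admits one split too many by the score test at IA1 (two by Wald, which against 0.0002 first passes at 8:45) and one at IA2 by either test. At 151 cases it changes no attainable split by either.

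The split comparisons assume equal person-time and ignore stratification; a fitted stratified Cox HR need not equal a/b. The exact conditional binomial method is only supportive (SAP 6.3.1.5) and is not used here as the deciding test.

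A reader might go further and infer that the trial was wrongly sized, that its error rate was inflated, or that the efficacy finding is in doubt. The documents do not support this. The 151 cases and crossing probabilities are mutually consistent, the rule applied was the p-value, and the actual first interim cleared a separately computed alpha.

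**What to change.** - Restate Table 7 on the event-split basis, and state the formula used for Tables 6, 7 and 15.
- Reconcile the Wald test in Table 26 with the score-based wording of Protocol 9.5.1.1 and the log-rank wording of Protocol 9.3 and SAP 4.3, naming the test that gives the decision p-value.
- In Protocol 9.6 and Table 15 and in SAP 6.4.1 and Table 4, mark the HR/VE values as a 4/d approximation subordinate to the nominal p-value, and note that they are too lenient at IA1 and IA2.
- Keep the original values visible, because Part A is complete and the pre-specified record should not be blurred.
- Leave the 151 cases, nominal alphas, crossing probabilities and p-value success rule unchanged.

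The cost is one recalculated table, notes on two others and on the sentences that translate p into HR, and one statement of the test. Some stated powers become less favourable. No participants, re-analysis or change of success rule are needed.
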